### **5.3.3. Sensitivity Analysis**

As a sensitivity analysis, a 2-sided 95% confidence interval using Wilson-Newcombe method will be presented.

## **5.4. Secondary Endpoint(s) Analysis**

### **5.4.1. Key Secondary Analysis**

The key secondary efficacy endpoint will be the proportion of participants gaining 3 lines or more from baseline in mesopic, high contrast, binocular DCNVA at Day 30, Hour 6. The key secondary efficacy parameter will be analyzed in the same way as the primary efficacy parameter.

AGN-190584

**5.4.2. Other Secondary Analyses**

Other secondary efficacy endpoints include:

1. Proportion of participants gaining 3-lines or more in mesopic, high contrast, binocular, DCNVA at Day 30, Hour 8.
2. Change from baseline in mesopic, high contrast, binocular DCNVA letters at Day 30, Hour 0.5.
3. Proportion of participants achieving 20/40 or better in photopic, high contrast, binocular, DCNVA at Day 30, Hour 1.
4. Change from baseline in Mesopic NVPTQ Performance score at Day 30, Hour 3.
5. Change from baseline in photopic, high contrast, binocular DCIVA letters at Day 30, Hour 3.
6. Proportion of participants gaining 3-lines or more in mesopic, high contrast, binocular, DCNVA at Day 30, Hour 10.
7. Change from baseline in mesopic, high contrast, binocular DCNVA letters at Day 30, Hour 0.25.
8. Proportion of participants achieving 20/40 or better in photopic, high contrast, binocular, DCNVA at Day 30, Hour 3.
9. Change from baseline in Mesopic NVPTQ Satisfaction score at Day 30, Hour 3.
10. Change from baseline in PICQ Coping score at Day 30, Hour 3.
11. Change from baseline in PICQ Impact score at Day 30, Hour 3.

All secondary endpoints related to proportion of participant gaining 3 lines or more or achieving 20/40 better (endpoints 1, 3, 6 and 8) will be analyzed with the same analysis method as the primary efficacy parameter.

Timepoints are defined as scheduled measurement times made for each visit. Change from baseline in mesopic, high contrast, binocular DCNVA letters (endpoints 2 and 7) will be analyzed using mixed-effects model with repeated measures (MMRM) by timepoint that includes treatment, visit, treatment by visit interaction, age group, baseline DCNVA severity, iris color, and emmetropes/non-emmetropes as factors as well as baseline DCNVA value, and baseline DCNVA value by visit interaction as covariates under the assumption of missing at random (MAR). An unstructured covariance matrix will be used as the covariance structure for

AGN-190584

repeated measurements. A sensitivity analysis will be implemented with the missing data imputed with the average outcome of the vehicle arm under the assumption of missing not at random (MNAR). Change from baseline in photopic, high contrast, binocular DCIVA letters (endpoints 4) will be analyzed with the similar way as change from baseline in mesopic, high contrast, binocular DCNVA letters. Baseline DCIVA will be included as the covariate instead of baseline DCNVA.

NVPTQ and PICQ scoring algorithms are provided in [Appendix 4](#). Change from baseline in the mesopic NVPTQ Performance score, Mesopic NVPTQ Satisfaction score, PICQ Coping score, and PICQ Impact score (endpoints 4, 9, 10 and 11) will be analyzed using an analysis of covariance (ANCOVA) model that includes treatment, age group, baseline DCNVA severity, iris color, emmetropes/non-emmetropes as factors as well as baseline PRO score as covariate. Also, the cumulative distribution function (CDF) curves will be presented for each of the change from baseline PRO domain scores. The CDF curves (one per domain score for a total of four) represent the cumulative proportion of patients with any particular level of CFB in PRO domain scores at Day 30 Hour 3, by treatment arm. Curves will be produced with a vertical line drawn at the responder threshold.

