8.1. Efficacy Assessments

Efficacy assessments are: mesopic and photopic, high contrast DCNVA for each eye and binocularly, mesopic and photopic, high contrast DCIVA for each eye and binocularly, PRO questionnaires (NVPTQ, PICQ,

AGN-190584

Table 8-1 Efficacy Assessments

Assessment	Timing	Measurement
Visual Acuity		
Mesopic, high contrast DCNVA for each eye and binocularly	
 • Screening • Days 1, 14, and 30: Hours 0, 0.25, 0.5, 1, 3, 6, 8, and 10 • Days 3 and 7: Hours 0, 1, and 3 	
 • Visual acuity for near (40-cm), intermediate (66-cm) and distance (4-meter) targets will be measured in mesopic and photopic conditions. • Mesopic condition is defined as lighting 3.2 to 3.5 candelas per square meter (cd/m^2; 10 to 11 lux) measured at the target. Photopic condition is defined as lighting $\geq 80 \text{ cd}/\text{m}^2$ (251 lux) measured at the target.
Photopic, high contrast DCNVA for each eye and binocularly	
 • Screening • Days 1, 14, and 30: Hours 0, 0.25, 0.5, 1, 3, 6, 8, and 10 • Days 3 and 7: Hours 0, 1, and 3 	
Mesopic and photopic, high contrast DCIVA for each eye and binocularly	
 • Screening • Days 1, 14, and 30: Hours 0, 1, 3, 6, 8, and 10 • Days 3 and 7: Hours 0, 1, and 3 	

AGN-190584

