9.4.1.3. Secondary Analyses

The key secondary efficacy endpoint is the proportion of participants gaining 3 lines or more in mesopic, high contrast, binocular DCNVA at Day 30, Hour 6.

The key secondary efficacy endpoint will be analyzed using a chi-square test. Missing data will be regarded as 3-line gain failure.

All analyses for other secondary efficacy endpoints will be based on observed data only. Secondary endpoints 1, 3, 6, and 8 will be analyzed using a chi-square test. Secondary endpoints 2, 4, 5, and 7 will be analyzed using MMRM with study intervention group, visit, visit by study intervention group interaction, age group, baseline binocular DCNVA severity, iris color, emmetropes/non-emmetropes, baseline value, and baseline value by visit interaction as fixed effects. The within-participant correlation error structure is unstructured. Secondary endpoints 9, 10, and 11 will be analyzed using analysis of covariance with study intervention group, age group, baseline binocular DCNVA severity, iris color, emmetropes/non-emmetropes, and baseline domain score as fixed effects.

AGN-190584

To control the overall Type 1 error rate in the efficacy analysis, a gatekeeping testing procedure will be used. Secondary efficacy endpoints will be tested only if the primary efficacy endpoint is statistically significant. A proper multiple comparison procedure will be pre-specified in the SAP.

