## 1.1. Study Design

Study 1883-302-013 is a multicenter, double-masked, randomized, vehicle-controlled, parallel group, phase 3 study evaluating the efficacy and safety of AGN-190584 (1.25% pilocarpine) dosed once daily, bilaterally, over a period of 30 days in participants with presbyopia. The study population will consist of adult male and female participants with objective and subjective evidence of presbyopia. Approximately 200 participants per group will be randomized.

Participants will be randomized in a 1:1 ratio to receive either AGN-190584 or vehicle dosed once daily, in each eye, for 30 days. This randomization will be stratified by age (2 groups:  $\leq 50$  years and  $> 50$  years), baseline binocular DCNVA (2 groups: 20/40 to 20/60 inclusively, and worse than 20/60), iris color (brown and non-brown), and emmetropes/non-emmetropes. This study consists of the following visits: screening (Days -30 to -1), Day 1 (baseline), and Days 3, 7, 14, and 30.

Study interventions, either AGN-190584 or vehicle will be administered as topical eye drop once daily. Following the study schema (Figure 1-1), study intervention will be administered by designated site personnel on visit days and at home by the participant in-between office visits, ideally prior to starting their day. On the day before office visits, the study intervention must be administered no less than 16 hours before the scheduled visit time.

[figure not shown]

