### **5.3.2. Main Analytical Approach**

The primary efficacy parameter will be analyzed using a chi-square test with 2-sided 95% confidence interval based on the normal approximation based on pooled variance without continuity correction.

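### The two photopic 20/40-or-better endpoints (H3, H8) are tested without baseline photopic DCNVA: valid, but power is given up that data already collected could recover

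*SAP*

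**What the plan says.** - **Endpoints.** SAP 5.4.2 lists endpoint 3 as "Proportion of participants achieving 20/40 or better in photopic, high contrast, binocular, DCNVA at Day 30, Hour 1" and endpoint 8 as "Proportion of participants achieving 20/40 or better in photopic, high contrast, binocular, DCNVA at Day 30, Hour 3". They are H3 and H8 in Table 5-1. Both are a status at Day 30, with no required gain and no restriction on baseline acuity. Protocol 9.4.1.1 defines them the same way.
- **Test.** SAP 5.4.2 says that the binary secondary endpoints "will be analyzed with the same analysis method as the primary efficacy parameter". SAP 5.3.2 gives that method: "The primary efficacy parameter will be analyzed using a chi-square test with 2-sided 95% confidence interval based on the normal approximation based on pooled variance". It has no covariate and no stratum. Protocol 9.4.1.3 agrees: "Secondary endpoints 1, 3, 6, and 8 will be analyzed using a chi-square test".
- **Baseline.** Protocol 8.1 includes "photopic, high contrast DCNVA for each eye and binocularly" among the efficacy assessments, and Table 8-1 schedules it at screening and at Day 1 Hour 0, before dosing.
- **Stratification.** SAP 1.1 stratifies randomisation by "baseline binocular DCNVA (2 groups: 20/40 to 20/60 inclusively, and worse than 20/60". A value of 20/40 is therefore admitted, and it shares a stratum with 20/60. The lighting condition is not stated.
- **Alpha.** The text under SAP Figure 5-1 tests H3 at 0.01. It leaves H1 and H6 untested unless every other hypothesis is rejected.

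**The concern.** H3 and H8 are the only tested efficacy endpoints in which baseline enters neither the definition nor the model. The 3-line endpoints are gains from baseline. The letter-change and questionnaire endpoints adjust for their own baseline in the MMRM or ANCOVA. For H3 and H8, acuity at entry probably explains much of who reaches 20/40 at Day 30, and the planned test leaves that variation in the error.

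Stratifying by the randomisation factor would recover only part of it, because that factor puts a participant at 20/40 together with one at 20/60.

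At stake is power at a strict alpha. If H3 or H8 fails, the Hour 8 and Hour 10 hypotheses (H1, H6) cannot be tested. A second matter is reading the result: the reported rates mix gains with acuity that was already present.

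**Working it through.** **1. The plan's own figure.** SAP section 3 assumes 8.8% vs 18.4% for the key secondary endpoint. With pooled rate 0.136,

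n = [1.960·√(2·0.136·0.864) + 0.842·√(0.088·0.912 + 0.184·0.816)]² / 0.096² = 199 per arm.

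Two hundred per arm gives 80.2% power at two-sided 5%, so the stated figure reproduces. The documents give no power or response rate for H3 or H8.

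**2. Inputs for H3.** From the documents: 200 per arm, 1:1 allocation, two-sided alpha 0.01 (critical value 2.576). Assumed, because the documents are silent: the share s already at 20/40 at baseline, the proportion of them still there at Day 30 (retention), and the success rates in the rest.

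**3. One case worked by hand.** Let s = 20%, retention 95% in both arms, and 48% vs 30% in the rest.

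- *Chi-square.* Overall rates: 0.2·0.95 + 0.8·0.48 = 0.574 and 0.2·0.95 + 0.8·0.30 = 0.430, a difference of 0.144 with pooled rate 0.502. Null SE = √(2·0.502·0.498/200) = 0.0500. Alternative SE = √[(0.574·0.426 + 0.430·0.570)/200] = 0.0495. Power = Φ[(0.144 − 2.576·0.0500)/0.0495] = Φ(0.31), about 62%.
- *CMH by baseline status.* There are 40 and 160 per arm in the two strata, so the weights n₁n₀/n are 20 and 80. Numerator: 20·0 + 80·0.18 = 14.4. Null variance: 20·0.95·0.05 + 80·0.39·0.61 = 19.98 (SD 4.470). Alternative variance: 0.95 + 80·(0.48·0.52 + 0.30·0.70)/2 = 19.33 (SD 4.397). Power = Φ[(14.4 − 2.576·4.470)/4.397] = Φ(0.66), about 74%.

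**4. Range over s.** Simulation with 40,000 trials per scenario, same retention and same rates in the rest. It agrees with the formulas to about one point.

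| Already at 20/40 | Chi-square | CMH |
|---|---|---|
| 0% | 87% | 87% |
| 2% | 85% | 86% |
| 5% | 82% | 85% |
| 10% | 76% | 82% |
| 20% | 63% | 74% |
| 30% | 49% | 66% |

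Much of the fall down the chi-square column is dilution: participants already at threshold add nothing to the difference. CMH recovers only part of it.

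**5. Other assumptions.**
- s = 20%, rest 58% vs 40%: 64% vs 72%.
- s = 20%, rest 38% vs 20%: 63% vs 81%, a gain of 18 points.
- Retention 80% instead of 95%: the gain falls from 6 to 3 points at s = 10%, and from 11 to about 5-6 at s = 20%.
- Rest 55% vs 30%: 98% vs 99% at s = 10%, and 93% vs 97% at s = 20%.

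**6. A second model.** Baseline and Day 30 acuity are taken as correlated normal variables (correlation 0.5 to 0.8), 2% to 40% are at threshold at baseline, and the effect is set for about 80% unadjusted power. There were 3,000 trials per scenario. Logistic regression on baseline letters (likelihood-ratio test) gained about 3 to 17 points, and CMH about 0 to 13. With correlation 0.7 and 25% at threshold, power was 80% (chi-square), 89% (CMH) and 94% (logistic). With everyone at threshold excluded at entry, the logistic gain was still about 3 to 9 points.

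**7. Type I error.** In the null scenarios of both models, every test rejected at about 1% (0.87% to 1.15% in the second model).

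**The case against.** The strongest reply is that nothing here is an error. The chi-square is specified in the protocol, holds its level, and randomisation keeps the comparison unbiased. Reaching 20/40 is a legitimate functional threshold. All of that stands.

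The size of the gain also depends on undocumented inputs. With few participants at threshold, lower retention or a large effect, the CMH gain shrinks to a few points or to nothing. That stands too. It favours regression on letters, whose gain does not need anyone to start at 20/40.

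A reader might infer more than the documents support:

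- *That some participants do meet the photopic threshold at entry.* The stratum boundary allows 20/40, but its lighting is not stated and not all entry criteria are visible in the public text. The number could be small.
- *That such participants succeed whatever the treatment.* They count only if they are still at 20/40 or better at Day 30.
- *That H8 depends on H3.* The text under Figure 5-1 opens H7, H8 or H9 after a rejection among five hypotheses. The figure is not shown, so neither the path to H8 nor its alpha can be read.

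Finally, the SAP contents list a section 5.7.2 on efficacy subgroups whose text is not visible. Whether a tabulation by baseline acuity is already planned cannot be judged.

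**Conclusion.** The point holds as a gain in efficiency and not as a fault in validity. The planned tests of H3 and H8 are sound, but they leave out a collected baseline measurement that should predict the outcome.

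At alpha 0.01 and 200 per arm, CMH by baseline status gains from about 0 points (0-2% at threshold) to about 17 (30% at threshold, 95% retention, 48% vs 30% in the rest), and 18 in one lower-rate scenario. Adjusting for baseline letters gains about 3 to 17 points. These are ranges under assumption: the share at threshold, the retention, the response rates and the correlation are not in the documents. No scenario showed a loss, and Type I error was unchanged. The analysed number will be below the number randomised, because SAP 5.1 removes one site from the efficacy analyses and uses observed data for these endpoints.

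**What to change.** Keep both endpoint definitions. Before unmasking:

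1. Pre-specify for H3 and H8 a logistic regression on treatment and baseline photopic binocular DCNVA letters (the last value before first dose, as in SAP 5.1). Report the standardised risk difference with a 95% confidence interval, and name the one test that gives the p-value used in the graphical procedure. CMH stratified by 20/40 or better at baseline, yes or no, is the simpler alternative, but it gains little if few participants are at threshold.
2. Record the departure from the protocol's chi-square in SAP Appendix 2 (section 6.2), which at present lists only the change to the primary endpoint.
3. Tabulate by arm the number at 20/40 or better at baseline, and the Day 30 rate among those who were worse.

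The cost is a revision of SAP 5.4.2 and 6.2 and some programming. No new data, visits or participants are needed. If unmasking has already happened, the adjusted analysis can only be supplementary.

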### **5.4.3. Multiplicity Adjustment**

[figure not shown]
The graphical procedure displayed in [Figure 5-1](#) will be employed to control the overall familywise error rate at  $\alpha=0.05$  for the following hypotheses testing. Let  $1r_y$ ,  $2r_y$ ,  $H1$ ,  $H2$ ,  $H3$ ,  $H4$ ,  $H5$ ,  $H6$ ,  $H7$ ,  $H8$ ,  $H9$ ,  $H10$ , and  $H11$  represent the treatment effect comparisons of AGN-190584 with vehicle. Details of the hypotheses and corresponding efficacy parameters are described in [Table 5-1](#).

AGN-190584

Table 5-1 Hypotheses and Corresponding Efficacy Parameters

Hypothesis	Efficacy Parameter
1yr	Proportion of participants gaining 3-lines or more in mesopic, high contrast, binocular, DCNVA without losing more than 5-letters of mesopic, high contrast, binocular CDVA with the same refractive correction at Day 30, Hour 3
2ry	Proportion of participants gaining 3-lines or more in mesopic, high contrast, binocular, DCNVA at Day 30, Hour 6
H1	Proportion of participants gaining 3-lines or more in mesopic, high contrast, binocular, DCNVA at Day 30, Hour 8
H2	Change from baseline in mesopic, high contrast, binocular DCNVA letters at Day 30, Hour 0.5
H3	Proportion of participants achieving 20/40 or better in photopic, high contrast, binocular, DCNVA at Day 30, Hour 1
H4	Change from baseline in photopic, high contrast, binocular DCIVA letters at Day 30, Hour 3
H5	Change from baseline in Mesopic NVPTQ Performance score at Day 30, Hour 3
H6	Proportion of participants gaining 3-lines or more in mesopic, high contrast, binocular, DCNVA at Day 30, Hour 10
H7	Change from baseline mesopic, high contrast, binocular DCNVA letters at Day 30, Hour 0.25
H8	Proportion of participants achieving 20/40 or better in photopic, high contrast, binocular, DCNVA at Day 30, Hour 3
H9	Change from baseline in Mesopic NVPTQ Satisfaction score at Day 30, Hour 3
H10	Change from baseline in PICQ Coping score at Day 30, Hour 3
H11	Change from baseline in PICQ Impact score at Day 30, Hour 3

AGN-190584

**Figure 5-1 Graphical Testing Procedure**

Specifically, 2ry, H2, H3, H4 and H5 will be tested at  $\alpha=0.01$  separately. If 2ry, H2, H3, H4 or H5 is rejected, H7, H8 or H9 will then be tested. If H9 is rejected, H10 and H11 will then be tested. H1 and H6 will be tested only if all other endpoints are significant.

AGN-190584

## **5.6. Safety Analyses**

The safety analyses will be performed using the safety population. The safety parameters will include AEs, vital signs (blood pressure and heart rate), mesopic and photopic, high contrast, CDVA, for each eye and binocularly, study intervention tolerability and drop comfort assessments, temporal/supraorbital headache assessment using VAS, IOP, slit-lamp biomicroscopy and near contrast sensitivity. For each safety parameter, the last non-missing safety assessment before the first dose of study intervention will be used as the baseline for all analyses of that safety parameter.

### **5.6.1. Extent of Exposure**

The exposure to study intervention, calculated as (last study intervention date - first study intervention date + 1), will be summarized using descriptive statistics by treatment for the safety population.

### **5.6.2. Adverse Events**

An AE will be considered a treatment emergent adverse event (TEAE) if the AE began or worsened (increased in severity or became serious) after the first administration of study intervention. However, an AE that occurs more than 30 days after the last administration of study intervention will not be counted as a TEAE.

The number and percentage of participants reporting TEAEs in each treatment group will be tabulated by descending percentage in any group, by SOC and PT, and further categorized by severity and causal relationship to the study intervention. If more than 1 AE is coded to the same PT for the same participant, the participant will be counted only once for that PT using the greatest severity and strictest causality for the summarization by severity and causal relationship.

The incidence of common ( $\geq 5\%$  of participants in any treatment group) TEAEs will be summarized by SOC, PT, and treatment group.

The total number of TEAEs by severity will be summarized by treatment group. The total number of TEAEs as well as headache of special interest by causal relationship to the study intervention will be summarized by treatment group. The number and percentage of participants reporting study intervention related TEAEs will be tabulated by SOC and PT.

An ocular AE is defined as the location of AE occurring in the eye. Ocular and nonocular headache of special interest will be summarized.

AGN-190584

A TESAE is defined as an SAE that is also a TEAE. The number and percentage of participants who have TESAEs will be summarized by PT and treatment group. In addition, the incidence of on-therapy SAEs that lead to death will be summarized separately by PT for each treatment group.

Summary tables will be provided for TEAEs leading to discontinuation and TESAEs. Listings of all TEAEs, SAEs, and AEs leading to discontinuation by participant will be presented.

### **5.6.3. Vital Signs**

Descriptive statistics for vital signs (systolic and diastolic blood pressure, and pulse rate) and changes from baseline values at each assessment timepoint will be presented by treatment group.

### **5.6.4. Mesopic, High Contrast, Binocular CDVA**

Change from baseline in number of letters in binocular mesopic, high contrast, CDVA will be summarized descriptively for each assessment timepoint by treatment group.

### **5.6.5. Photopic, High Contrast, Binocular CDVA**

Change from baseline in number of letters in binocular photopic, high contrast, CDVA will be summarized descriptively for each assessment timepoint by treatment group.

### **5.6.6. Study Intervention Tolerability and Drop Comfort Assessments**

Ocular tolerability assessment will be performed at each visit. Symptoms of blurred vision, foreign body sensation, pain, burning/stinging, tearing, and itching will be assessed using a 5-point scale (0 = none, 0.5 = trace, 1 = mild, 2 = moderate, and 3 = severe) for the severity and a 3-point scale (<1 min, 1 to 5 min, and >5 min) for the duration. Drop comfort will be assessed using a 6-point scale (soothing, very comfortable, comfortable, uncomfortable, very uncomfortable, and intolerable). For the severity, duration, and drop comfort, the number and percentage of participants in each category will be tabulated for each time point by treatment group.

### **5.6.7. Temporal/Supraorbital Headache Visual Analog Scale**

Temporal and supraorbital headache will be separately assessed for each eye using a VAS at each visit. The reported values and the changes from baseline will be summarized using descriptive statistics for each time point for each eye by treatment group.

AGN-190584

**5.6.8. Intraocular Pressure**

IOP is measured for each eye using the Goldmann applanation tonometer at each visit. Tabulations will be based on the worst change (greater increase from baseline) between 2 eyes assessed at each visit. Descriptive statistics for IOP and changes from baseline at each assessment timepoint will be presented by treatment group.

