2.2. Background

The impairment of near vision is common among older adults. In 2005, 1.044 billion people globally were estimated to have presbyopia, and prevalence is expected to increase to 1.782 billion by 2050 (Holden 2008). Both nonsurgical and surgical methods for the correction of presbyopia are available. Traditional nonsurgical methods of refractive correction for presbyopia include the use of dedicated reading spectacles, bifocal or varifocal spectacles, and monovision or multifocal contact lenses. A number of surgical techniques are also used for the treatment of presbyopia, which include monovision PRK or LASIK, conductive keratoplasty, intraocular lenses, and corneal inlays. However, for each of the existing technologies mentioned above, visual quality is reduced at 1 or more viewing distances, and each comes with its own unique safety risks and associated complications. For example, bifocals and progressive lenses (eg, reading glasses, contacts) produce optical aberrations and can increase the risk of falls (Johnson 2007, Lord 2002). Multifocal optics reduce image quality uniformly at all viewing distances. For surgical technologies, surgical risks, and the need for repositioning and explantation, or regression of effect have limited their widespread adoption (Moshirfar 2017, Ruiz 2009, Tomita 2015). Thus, there remains a need for a noninvasive, reversible, pharmacological treatment for presbyopia.

Pilocarpine is a muscarinic receptor agonist that mimics the actions of the parasympathetic neurotransmitter, acetylcholine, on smooth muscle. This causes 2 effects that enhance near vision: 1) constriction of the iris sphincter muscle, resulting in pupil constriction (miosis), and 2) contraction of the ciliary muscle, resulting in central lens steepening and lens accommodation (focusing from distance to near) (García-Lázaro 2012). Reducing the pupil size has long been recognized as an effective way to increase the useful depth of focus, in part by reducing peripheral aberrations (Tucker 1975).

Pilocarpine ophthalmic solutions are currently used for the reduction of elevated IOP in patients with open-angle glaucoma or ocular hypertension, management of acute-angle closure glaucoma,

AGN-190584

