6.1. Study Intervention(s) Administered

Study Intervention Name	AGN-190584	Vehicle
Dosage Formulation	Topical eye drop	Topical eye drop
Identity of Formulation	Pilocarpine HCl 1.25% Ophthalmic Solution [REDACTED]	Pilocarpine HCl Placebo Ophthalmic Solution
Drug Substance	Pilocarpine 1.25%	Not applicable
Route of Administration	Topical eye drop	Topical eye drop
Dosing Instructions	1 drop in each eye once daily	1 drop in each eye once daily
[REDACTED]		
Manufacturer	Allergan Sales, LLC.	Allergan Sales, LLC.
Number and Timing of Interventions	1 drop bilaterally, once daily	1 drop bilaterally, once daily
[REDACTED]		

As this is a double-masked study, AGN-190584 and Vehicle will be supplied in identically appearing bottles and cartons.

[REDACTED]
AGN-190584

Approval Date: 06-Mar-2020

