8.2.6. Temporal/Supraorbital Headache Visual Analog Scale

Participants will be asked to rate the degree of temporal and supraorbital headache experienced after the second eye is instilled with a drop of study intervention, for the right and left eyes separately. Headache will be reported on an unmarked 100-mm wide VAS, ranging from no pain on the left to worst possible pain on the right.

[REDACTED]
AGN-190584**8.2.7. Intraocular Pressure**

IOP must be measured after the biomicroscopic exam is completed and prior to pupil dilation. Measurements will be taken using a Goldmann applanation tonometer affixed to a slit-lamp with the participant seated. The participant and slit-lamp should be adjusted so that the participant's head is firmly positioned on the chin rest and against the forehead rest without leaning forward or straining. Tight fitting neckwear should be loosened. Both eyes will be tested, with the right eye preceding the left eye. The measurer will look through the binocular viewer of the slit lamp at low power. The tension knob will be preset at a low-pressure value (4 to 6 mm Hg). The measurer will follow the image of the fluorescein stained semicircles while slowly rotating the tension knob until the inner borders of the fluorescein rings touch each other at the midpoint of their pulsation in response to the cardiac cycle. When this image is reached, the measurer will take his/her fingers off the tension knob and record the IOP reading along with the date and time of day.

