## 5. Statistical Analyses

### 5.1. General Considerations

- Efficacy endpoints will be analyzed using the ITT population, and the safety endpoints will be analyzed using the safety population.
- The baseline for efficacy and safety will be the last non-missing assessment prior to the first administration of study intervention. For participants who were randomized but not treated, the baseline value will be the assessment collected on or prior to the randomization date, whichever is later.
- The change from baseline values will be computed as the postbaseline value minus the baseline value.
- Continuous variables will be summarized by number of participants with observed values (n), mean, standard deviation (SD), median, 1st and 3rd quartiles (Q1, Q3), minimum (min), and maximum (max).
- Categorical variables will be summarized by number of participants with observed values or events (n), frequency count (n1) and percentage of participants with observed values or events.
- All statistical hypothesis tests will be performed at the 2-sided 5% significance level, unless stated otherwise. All confidence intervals will be at least 2-sided 95% confidence intervals.
- In general, statistical analyses will be performed using SAS version 9.4 or higher. MedDRA version 22.1 or higher will be used to code adverse events, biomicroscopy, and medical history. WHODRUG Enhanced B2 will be used to code medications.

To control the overall Type 1 error rate in the efficacy analysis, a gatekeeping testing strategy will be used. All secondary efficacy endpoints will be tested only if the primary efficacy endpoint is statistically significant and the testing procedures are described in the graphical procedure in [Figure 5-1](#).

For primary and key secondary analyses, participants with missing data will be regarded as non-responders. Analyses for other secondary efficacy endpoints will be based on observed data only.

Per confirmation of the site, DCNVA measurements were not conducted correctly for participants at investigator site 051 at screening visit and baseline visit (Day 1 Hour 0). In error, the participants were corrected for near vision rather than distance vision when these

AGN-190584

measurements were taken. Therefore, it is decided to exclude all participants from this site from efficacy analyses. These participants will be included in all safety analyses.

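### SAP 5.6.8 averages IOP over whichever eye rose more at each visit, which shifts every arm's mean change upward; per-eye or two-eye-average means should be added (minor, descriptive safety table)

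*SAP*

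**What the plan says.** IOP is a safety measure in both documents. Protocol 8.2.7 has it taken in each eye ("Both eyes will be tested, with the right eye preceding the left eye"), and Protocol 6.1 has both eyes dosed in both arms ("1 drop in each eye once daily").

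SAP 5.6.8 first gives the eye-selection rule: "Tabulations will be based on the worst change (greater increase from baseline) between 2 eyes assessed at each visit". It then names the output: "Descriptive statistics for IOP and changes from baseline at each assessment timepoint will be presented by treatment group".

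SAP 5.1 defines that output ("Continuous variables will be summarized by number of participants with observed values (n), mean, standard deviation (SD), median, 1st and 3rd quartiles", followed by minimum and maximum) and the sign of a change ("The change from baseline values will be computed as the postbaseline value minus the baseline value"), so a positive value is a rise.

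SAP 5.6.8 contains no per-eye summary, no two-eye average and no count of participants above a threshold. The headache scale, which is also collected for each eye, is handled differently in SAP 5.6.7: "The reported values and the changes from baseline will be summarized using descriptive statistics for each time point for each eye by treatment group".

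**The concern.** The eye is chosen after the measurement, separately at each visit, because its change is the larger of the two. A mean taken over eyes chosen this way is the mean worst-eye change. It is not the mean IOP change in the arm, although a reader of a table of change from baseline would take it as such.

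Two things follow. An arm in which nothing happens shows a positive mean change, and a small true fall is shown as smaller than it was or as a rise. In addition, the selected eye can switch between visits, so the IOP values and baselines behind successive columns need not come from the same eyes. At baseline itself there is no change by which to select an eye. Section 5.6.8 does not say what happens with ties or with one missing eye.

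The stake is the reading of a by-arm descriptive safety table.

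**Working it through.** The documents give no IOP figure, so there is no plan figure to reproduce. The direction of the shift follows from the rule alone. Its size needs two inputs that must be assumed.

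**Direction, without distributional assumptions.** Write R and L for one participant's right-eye and left-eye change at a visit. Then

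max(R, L) = (R + L)/2 + |R - L|/2.

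The second term is never negative. The tabulated mean therefore exceeds the mean two-eye change by half the mean absolute difference between the eyes. The excess is zero only if the two eyes always change by the same amount.

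**Size under normality.** Let both eyes have mean change mu, SD s and between-eye correlation rho. R - L then has mean 0 and variance 2s²(1 - rho), and half its mean absolute value is

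shift = s x sqrt((1 - rho)/pi).

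**Inputs**
- s: assumed, 1.5 to 3.0 mm Hg (central value 2.5)
- rho: assumed, 0.5 to 0.9 (central value 0.7)
- participants per arm: about 200 (SAP 1.1)

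**Shift in mm Hg**

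| s | rho 0.5 | rho 0.7 | rho 0.8 | rho 0.9 |
|---|---|---|---|---|
| 1.5 | 0.60 | 0.46 | 0.38 | 0.27 |
| 2.0 | 0.80 | 0.62 | 0.50 | 0.36 |
| 2.5 | 1.00 | 0.77 | 0.63 | 0.45 |
| 3.0 | 1.20 | 0.93 | 0.76 | 0.54 |

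A simulation of 2,000,000 pairs with changes rounded to 1 mm Hg agrees. At s = 2.5 and no true change, the worst-eye mean is 1.00, 0.77, 0.63 and 0.45 across the row, while the two-eye average stays at about 0.

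**What one arm's table would show (s = 2.5, rho = 0.7)**
- True change 0: 0 + 0.77 = +0.77. The SD of the larger change is 2.5 x sqrt(1 - 0.3/pi) = 2.38, so the standard error with 200 participants is 2.38/sqrt(200) = 0.168. The shift is 0.77/0.168 = about 4.6 standard errors.
- True change -0.5: shown as +0.27.
- True change -1.0: shown as -0.23.

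Over the whole assumed range, a true change of -1.0 is shown as anything from -1.0 + 0.27 = -0.73 to -1.0 + 1.20 = +0.20.

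**Difference between arms.** With the same s and rho in both arms the shift cancels, and a true difference of -1.0 is shown as -1.0. If they differ, the error is the difference of the two shifts:
- drug s 3.0, vehicle s 2.5, both rho 0.7: error +0.155, so -1.0 is shown as about -0.85 (-0.845)
- drug rho 0.5, vehicle rho 0.8, both s 2.5: error +0.367, so -1.0 is shown as -0.63
- drug s 2, rho 0.8, vehicle s 3, rho 0.5: error -0.692, so -1.0 is shown as -1.69

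These unequal cases are illustrations. Nothing in the documents suggests that the arms differ in this way.

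**The case against.** **The rule may be meant for counts only.** Elsewhere in the safety section (SAP 5.6.2, 5.6.6, 5.6.9) the SAP uses tabulating for numbers and percentages, while continuous measures are summarized or presented. On that usage the worst-eye rule could apply to a categorical table, where it fits well. However, 5.6.8 defines no such table, so the rule has only the descriptive statistics to attach to. The table specifications are in a separate document (SAP 1) that is not available here, so the final layout cannot be confirmed. This part stands as a reason to clarify the wording.

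**A worst-eye mean is unbiased for what it is.** This is true. For a safety measure where a rise is the worry, choosing the greater increase errs toward showing harm and is a legitimate conservative view. The difficulty is that it is the only view planned and nothing in 5.6.8 requires it to be labelled.

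**The vehicle arm shows the same shift.** This also stands. A reader who compares the arms is largely protected if variability and between-eye correlation are similar.

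**A fall in IOP is not an expected finding here.** A reader might infer from Protocol 2.2 ("Pilocarpine ophthalmic solutions are currently used for the reduction of elevated IOP in patients with open-angle glaucoma or ocular hypertension") that the rule will conceal a known pressure-lowering effect. The documents do not support that. The sentence concerns patients with elevated pressure, whom exclusion criterion 4.07 keeps out. Neither document gives an expected fall in this population or makes pressure lowering an objective.

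**Conclusion.** The point holds in a limited form. As SAP 5.6.8 reads, each arm's mean IOP change is at or above its mean two-eye change by construction, and the eye behind each figure can change between visits. The direction needs no outside information. The size, about 0.3 to 1.2 mm Hg, rests on an assumed per-eye SD of 1.5 to 3.0 mm Hg, an assumed between-eye correlation of 0.5 to 0.9, normality, and equal means and SDs in the two eyes.

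Two stronger readings should be avoided. It does not follow that the table will show a rise where pressure fell: at the low end of the range, a true fall of 1.0 would still read as -0.73. Nor does it follow that the comparison with vehicle is distorted, since that needs unequal variability or correlation, for which there is no evidence in the documents. IOP is descriptive, so no efficacy test, significance level or power calculation is touched. This is a minor, cheap improvement to a safety table.

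**What to change.** In SAP 5.6.8:

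- Present mean IOP and mean change from baseline for the right and left eye separately, as SAP 5.6.7 does for the headache scale, or for each participant's two-eye average.
- Keep the worst-eye rule, labelled as such, for the maximum increase and for counts of participants with an increase.
- For the worst-eye output, state how ties and a single missing eye are handled.

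The cost is a few sentences in the SAP and one extra table. Both eyes are already measured, so no new data are needed, and the conservative view of the worse eye is kept.
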